## 8.1.1.1 AE reporting of overdose of BGJ398

Overdose of BGJ398 is to be reported as an AE when drug is administered or taken at a dose ≥200 mg and the overdose is associated with signs or symptoms. Overdose should follow the same reporting requirements as SAEs.

Confidential

### 8.1.1.2 Hy's Law

Additionally, potential drug induced liver injury that meets the following criteria (elevation of bilirubin and ALT/AST that meet Hy's Law criteria [FDA Guidance for Industry 2009]):

- Treatment-emergent ALT or AST >3 × baseline value in combination with total bilirubin  $\ge$ 2 × ULN (of which  $\ge$ 35% is direct bilirubin)
- Treatment-emergent ALT or AST >3 × baseline value in combination with clinical jaundice.

and is suspected or confirmed drug-induced liver injury, according to Hy's law criteria, requires reporting as an SAE.

# 8.1.1.3 Progression of underlying malignancy should be reported as AE only in special circumstances

**Progression of underlying malignancy is not reported as an adverse event** if it is clearly consistent with the suspected progression of the underlying cancer as defined by RECIST criteria, or other criteria as determined by protocol. Hospitalization **solely** due to the progression of underlying malignancy should NOT be reported as a serious adverse event. Clinical symptoms of progression may be reported as adverse events if the symptom cannot be determined as exclusively due to the progression of the underlying malignancy or does not fit the expected pattern of progression for the disease under study.

Symptomatic deterioration may occur in some patients. In this situation, progression is evident in the patient's clinical symptoms, but is not supported by the tumor measurements. Or, the disease progression is so evident that the investigator may elect not to perform further disease assessments. In such cases, the determination of clinical progression is based on symptomatic deterioration. These determinations should be a rare exception as every effort should be made to document the objective progression of underlying malignancy.

If there is any uncertainty about an adverse event being due only to the disease under study, it should be reported as an AE or SAE.

### 8.1.2 Laboratory test abnormality

Abnormal laboratory values or test results occurring after informed consent constitute adverse events only if they induce clinical signs or symptoms, are considered clinically

significant, require therapy (eg, hematologic abnormality that requires transfusion or hematological stem cell support), or require changes in study medication(s). Laboratory abnormalities that constitute an Adverse event in their own right should be recorded on the Adverse Events eCRF. Whenever possible, a diagnosis, rather than a symptom should be provided (e.g. anemia instead of low hemoglobin). Laboratory abnormalities that meet the criteria for Adverse Events should be followed until they have returned to normal or an adequate explanation of the abnormality is found. When an abnormal laboratory or test result corresponds to a sign/symptom of an already reported adverse event, it is not necessary to separately record the lab/test result as an additional event.

Laboratory abnormalities, that do not meet the definition of an adverse event, should not be reported as adverse events. A Grade 3 or 4 event (severe) as per CTCAE v4.0 does not automatically indicate a SAE unless it meets the definition of serious as defined below and/or as per investigator's discretion. A dose hold or medication for the lab abnormality may be required by the protocol and is still, by definition, an adverse event.

#### 8.2 Serious adverse events

#### 8.2.1 Definitions

Serious adverse event (SAE) is defined as one of the following:

- Is fatal or life-threatening
- Results in persistent or significant disability/incapacity
- Constitutes a congenital anomaly/birth defect
- Is medically significant, ie, defined as an event that jeopardizes the patient or may require medical or surgical intervention to prevent one of the outcomes listed above
- Requires inpatient hospitalization or prolongation of existing hospitalization, unless hospitalization is for:
  - a. Routine treatment or monitoring of the studied indication, not associated with any deterioration in condition
  - b. Elective or pre-planned treatment for a pre-existing condition that is unrelated to the indication under study and has not worsened since signing the informed consent
  - c. Treatment on an emergency outpatient basis for an event not fulfilling any of the definitions of a SAE given above and not resulting in hospital admission
  - d. Social reasons and respite care in the absence of any deterioration in the patient's general condition

In addition, any suspected transmission of an infectious agent via a medicinal product will be considered an SAE at study centers in the EU.

Progression of underlying malignancy is not reported as an adverse event if it is clearly consistent with the suspected progression of the underlying cancer as defined by RECIST criteria, or other criteria as determined by protocol. Hospitalization due solely to the progression of underlying malignancy should NOT be reported as a serious adverse event.

Clinical symptoms of progression may be reported as adverse events if the symptom cannot be determined as exclusively due to the progression of the underlying malignancy or does not fit the expected pattern of progression for the disease under study.

Symptomatic deterioration may occur in some patients. In this situation, progression is evident in the patient's clinical symptoms, but is not supported by the tumor measurements. Or, the disease progression is so evident that the investigator may elect not to perform further disease assessments. In such cases, the determination of clinical progression is based on symptomatic deterioration. These determinations should be a rare exception as every effort should be made to document the objective progression of underlying malignancy.

If there is any uncertainty about an adverse event being due only to the disease under study, it should be reported as an AE or SAE.

## 8.2.2 Reporting

For patients whose FGFR2 gene fusions or other FGFR genetic alteration status is unknown, SAE collection will start upon signing the molecular pre-screening ICF. SAEs will only be reported if the event is suspected to be causally related to a study procedure as assessed by the investigator (e.g. an invasive procedure such as biopsy). SAEs will be followed until resolution or until clinically relevant improvement or stabilization. If the main ICF is not signed (molecular screen failure), SAE collection ends 30 days after the last study related procedure. If the main ICF is signed, SAE collection is as below.

Patients with known FGFR2 gene fusions or translocations/other FGFR genetic alteration status who do not sign the molecular pre-screening ICF, SAE collection starts at the time of signing main study informed consent regardless of whether the patient is found to be a screen failure.

To ensure patient safety, every SAE, **regardless of suspected causality**, occurring after the patient has provided informed consent and until at least 30 days after the patient has stopped study treatment must be reported to Covance Safety (email: [contact]; [contact]) within 24 hours of learning of its occurrence. Any SAEs experienced after this 30 days period should only be reported to Covance Safety if the investigator suspects a causal relationship to the study treatment. Any additional information for the SAE including recurrent episodes, complications, or progression of the initial SAE must be reported as follow-up to the original episode within 24 hours of the investigator receiving the follow-up information. An SAE

occurring at a different time interval or otherwise considered completely unrelated to a previously reported one should be reported separately as a new event.

Confidential

Information about all SAEs is collected and recorded on the Serious Adverse Event Report Form; all applicable sections of the form must be completed in order to provide a clinically thorough report. The investigator must assess and record the relationship of each SAE to each specific study treatment (if there is more than one study treatment), complete the SAE Report Form in English, and submit the completed form within 24 hours to Covance Safety (email: [contact]; [contact]). Detailed instructions regarding the submission process and requirements for signatures are to be found in the investigator folder provided to each site.

Follow-up information is submitted in the same way as the original SAE Report. Each reoccurrence, complication, or progression of the original event should be reported as a follow-up to that event regardless of when it occurs. The follow-up information should describe whether the event has resolved or continues, if and how it was treated, whether the blind was broken or not, and whether the patient continued or withdrew from study participation.

If the SAE is not previously documented in the Investigator's Brochure or Package Insert (new occurrence) and is thought to be related to the study treatment, a Covance Safety associate may urgently require further information from the investigator for Health Authority reporting. Covance Safety may need to issue an Investigator Notification (IN), to inform all investigators involved in any study with the same drug that this SAE has been reported. Suspected Unexpected Serious Adverse Reactions (SUSARs) will be collected and reported to the competent authorities and relevant ethics committees in accordance with Directive 2001/20/EC or as per national regulatory requirements in participating countries.

## 8.3 Emergency blinding of treatment assignment

Not applicable.

#### 8.4 Pregnancies

To ensure patient safety, each pregnancy occurring while the patient is on study treatment (and for 30 days after the last study drug dose) must be reported to Covance Safety (email: [contact]; [contact]) within 24 hours of learning of its occurrence. The pregnancy should be followed up to determine outcome, including spontaneous or voluntary termination, details of the birth, and the presence or absence of any birth defects, congenital abnormalities, or maternal and/or newborn complications.

Pregnancy of a patient or partner of a male patient should be entered on the Pregnancy Notification CRF and reported by the investigator to Covance Safety (email: [contact]; [contact]). Pregnancy follow-up should be documented on a paper Pregnancy Follow-up Form and reported to Covance Safety as above. Any SAE experienced during pregnancy must be reported on the SAE Report Form.

Pregnancy outcomes must be collected for the female partners of any males who took study treatment in this study. Consent to report information regarding these pregnancy outcomes should be obtained from the mother.

Confidential

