  - Unstable angina pectoris or acute myocardial infarction ≤ 3 months prior to starting study drug
  - QTcF > 470 msec (males and females)
  - History of congenital long QT syndrome
- 16. Pregnant or nursing (lactating) women, where pregnancy is defined as the state of a female after conception and until the termination of gestation, confirmed by a positive hCG laboratory test
- 17. Women of child-bearing potential (WOCBP), defined as all women physiologically capable of becoming pregnant, unless they are using barrier contraception and a second form of highly effective contraception during dosing and for 3 months following the discontinuation of study treatment.

WOCBP and males whose sexual partners are WOCBP must agree to use barrier contraception and a second form of highly effective contraception (Clinical Trials Facilitation Group 2014; see Appendix 5 [Section 14.5]) while receiving study drug and for 3 months following their last dose of study drug. Alternatively, total abstinence is also considered a highly effective contraception method when this is in

line with the preferred and usual lifestyle of the patient. Periodic abstinence (eg, calendar, ovulation, symptothermal, post-ovulation methods) and withdrawal are not acceptable methods of contraception.

A woman is not of child-bearing potential if she has undergone surgical sterilization (total hysterectomy, or bilateral tubal ligation or bilateral oophorectomy at least 6 weeks before taking study drug) or if she is postmenopausal and has had no menstrual bleeding of any kind including menstrual period, irregular bleeding, spotting, etc., for at least 12 months, with an appropriate clinical profile, and there is no other cause of amenorrhea (eg, hormonal therapy, prior chemotherapy).

- 18. Sexually active males unless they use a condom during intercourse while taking drug and for 3 months after the last dose of the study drug and should not father a child in this period. A condom is required to be used also by vasectomized men as well as during intercourse with a male partner in order to prevent delivery of the drug via seminal fluid.
- 19. Have amylase or lipase  $> 2.0 \times ULN$ .
- 20. Have any known hypersensitivity to calcium-lowering agents, infigratinib, or their excipients.

## 6.1.1 Additional exclusion criteria for Cohort 3

21. Known existence of a V564F mutation in the FGFR2 gene.

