#### 7.2.2.6.5 Pregnancy and assessments of fertility

All WOCBP (pre-menopausal or less than 1 year after the onset of menopause) must have a serum pregnancy test  $(\beta-hCG) \le 72$  hours before the first dose of study treatment. Additionally, a serum pregnancy test should be performed at Day 1 of each cycle and at the End of Treatment visit.

Table 9: Clinical laboratory parameters collection plan

Test Category	Test Name
Hematology	Hematocrit, Hemoglobin, Red blood cell count, Platelets, White blood cells, Differential (Basophils, Eosinophils, Lymphocytes, Monocytes, Neutrophils)
Biochemistry	Albumin, Alkaline phosphatase, ALT (SGPT), AST (SGOT), Calcium (can be corrected), Chloride, Creatinine, Blood Urea Nitrogen (BUN), Potassium, Sodium, Magnesium, Phosphate.
	Direct Bilirubin, Indirect Bilirubin, Total Bilirubin, Lipid profile (Total Cholesterol, Triglycerides), Total Protein, Urea, Uric Acid, Amylase, Lipase
Urinalysis	Macroscopic Panel (Dipstick) (Blood, Glucose, Ketones, pH, Protein, Specific Gravity).
	Microscopic Panel (Red Blood Cells, WBC)
Coagulation	Prothrombin time (PT) or International normalized ratio [INR]), Partial thromboplastin time (PTT)
Pregnancy Test	Serum hCG at screening; day 1 of each cycle, EOT and other times points

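### The time-bound pregnancy-reporting rule stops 30 days after the last dose while contraception is required for 3 months, so about two-thirds of the post-treatment contraception window lies outside it, most clearly for female patients

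*Protocol*

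**What the plan says.** Section 8.4 of the protocol opens with a rule that has a clock: a pregnancy that occurs on study treatment "and for 30 days after the last study drug dose) must be reported to Covance Safety", within 24 hours of the site learning of it.

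Section 5.3 sets a longer post-treatment period, and does so three times:

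- Criterion 17, women of child-bearing potential: two forms of contraception "during dosing and for 3 months following the discontinuation of study treatment".
- The paragraph that follows, covering these women and men whose partners could become pregnant: contraception "while receiving study drug and for 3 months following their last dose of study drug".
- Criterion 18, sexually active men: condom use "for 3 months after the last dose of the study drug and should not father a child in this period".

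Two further sentences in 8.4 carry no time limit. One concerns notification: "Pregnancy of a patient or partner of a male patient should be entered on the Pregnancy Notification CRF". The other concerns outcomes: "Pregnancy outcomes must be collected for the female partners of any males who took study treatment in this study".

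Two other provisions bear on the period after day 30. Section 7.2.2.6.5 says that "a serum pregnancy test should be performed at Day 1 of each cycle and at the End of Treatment visit", and nothing later is scheduled. Section 8.2.2 says: "Any SAEs experienced after this 30 days period should only be reported to Covance Safety if the investigator suspects a causal relationship".

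**The concern.** The contraception requirement shows that the protocol wants conception avoided for 3 months after the last dose, by patients and by partners. Section 11.3 tells women that the risk to a fetus is unknown. If contraception fails between day 31 and the end of month 3, the pregnancy falls in a period that the protocol itself treats as one to guard, yet the only reporting rule with a deadline has already expired.

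What is at stake is the completeness of a small safety record. The number of pregnancies begun soon after treatment is the denominator for any statement about their outcome. If sites report late pregnancies mainly when something goes wrong, normal births and terminations drop out and the remaining record is selective. No efficacy endpoint and no planned analysis in the SAP depends on this.

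**Working it through.** The documents give no figure for this point, so there is none to reproduce. The check compares windows and then looks for other provisions that might cover the gap.

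**Inputs**

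- Reporting window after the last dose, R = 30 days (section 8.4).
- Contraception window after the last dose, C = 3 months (section 5.3, criteria 17 and 18). The protocol does not convert this to days. I assume 90 days, with a range of 84 to 92.

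**Share of the post-treatment window outside the time-bound rule:** (C − R) / C

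- C = 84: (84 − 30) / 84 = 54/84 = 64.3%
- C = 90: (90 − 30) / 90 = 60/90 = 66.7%
- C = 92: (92 − 30) / 92 = 62/92 = 67.4%

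**Sensitivity to the denominator.** Pregnancies on treatment are covered, so the two-thirds applies only to the period after the last dose. If days on treatment (T) are added to the denominator, with C = 90, the share is 60 / (T + 90). For assumed treatment lengths:

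- T = 28: 60/118 = 51%
- T = 84: 60/174 = 34%
- T = 175: 60/265 = 23%

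**Do other provisions cover day 31 to month 3?**

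- *Testing.* The last scheduled pregnancy test is at the End of Treatment visit, which section 4.1 places within 14 days of the decision to stop. No scheduled test would detect a later conception.
- *Safety follow-up.* Section 7.1.6 collects adverse events for 30 days after the last dose, the same boundary as the pregnancy rule.
- *Serious adverse events.* A congenital anomaly is serious under section 8.2.1. After 30 days it must be reported if the investigator suspects the drug. Section 8.4 also requires a report, with no stated window, of any serious event during pregnancy. These routes catch some adverse outcomes. They do not catch the pregnancy itself, nor an uneventful one.
- *Notification sentence in 8.4.* It has no time limit and names both patients and partners. It could be read as reaching beyond 30 days, but it does not say so, and the sentence before it sets a limit.
- *Outcome sentence in 8.4.* It is mandatory, has no time limit and covers partners of any treated man. It has no counterpart for female patients outside the 30-day rule: the general instruction to follow a pregnancy to its outcome sits in the paragraph that carries the 30-day limit.

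For partners, then, an untimed obligation exists beside the 30-day rule. For female patients, only the untimed notification sentence and the serious-event routes remain.

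**After alignment.** With R = C, the share is (90 − 90) / 90 = 0%.

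**The case against.** The strongest counter-case is that 8.4 should be read as a whole. On that reading the first sentence only fixes which pregnancies carry the 24-hour deadline, and the later paragraphs are broader. This argument largely stands for partners, since the outcome sentence is mandatory and unlimited. For female patients it turns a clear gap into an ambiguous one: two readings are open and sites may follow different ones.

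Second, contraception and expedited reporting are separate obligations, and nothing in the documents says their durations must agree. Thirty days is also the protocol's general safety boundary. This is fair: the mismatch is not an error of logic, and alignment is a matter of good practice. But no reason is given for choosing the shorter period, and the choice leaves out pregnancies that the contraception rule was written to prevent.

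Third, the two-thirds is a share of calendar days, not of pregnancies. That is correct. The documents give no basis for an expected count, and I assume that it is small in this population.

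A reader might go further and infer that pregnancies after day 30 go unreported, or that their outcomes need not be followed. The documents do not support that. The two untimed sentences in 8.4, and the continued reporting of late serious events with suspected causality, leave routes open.

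**Conclusion.** The mismatch is real, and it is a minor point. Roughly 60 of the 90 days of post-treatment contraception (64% to 67%, depending on how 3 months is counted) lie outside the mandatory, time-bound reporting rule. The gap is clearest for female patients and is substantially narrowed for partners.

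The figure assumes that the windows are compared from the last dose, and that a pregnancy is placed by the day it begins. Section 8.4 does not say whether onset or detection counts. The figure says nothing about how many pregnancies would be missed, and it does not imply that any particular contraception period is right.

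**What to change.** Reconcile section 8.4 with criteria 17 and 18 in section 5.3:

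1. Make the post-treatment reporting window in the first sentence of 8.4 match the protocol's own post-treatment contraception window, for patients and for partners.
2. State that the notification sentence and the partner-outcome sentence are not cut off at 30 days. Changing the number alone would leave 8.4 with timed and untimed sentences still unreconciled.

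No new visit is needed. Patients are already followed for survival at least every 4 months after treatment (section 7.1.6), so a question about pregnancy at the first of these contacts could cover the period.

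The cost is a few sentences in a written amendment, with the ethics approval that section 12.1 requires, and a few more reports to process. If the sponsor prefers to keep 30 days, it should give the reason in 8.4 and say plainly what sites are to do with a pregnancy that begins later.

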## 8.5 Warning and precautions

No evidence available at the time of this writing indicated that special warnings or precautions were appropriate, other than those noted in the current Investigator's Brochure. Additional safety information collected between IB updates will be communicated in the form of Investigator Notifications. This information will be included in the patient informed consent and should be discussed with the patient during the study as needed.

### 8.6 Data monitoring committee

A Data Monitoring Committee (DMC) will not be in place for this trial: a DMC is considered not feasible due to the short duration of the study. However, measures are put in place for monitoring the safety of the patients participating in this part of the study:

 Prompt review of safety data and constant monitoring for emerging safety signals by participating study sites and QED Therapeutics Personnel. As for any other study conducted by QED Therapeutics, any SUSAR and/or new safety signals will be promptly communicated to all participating investigators and Health Authorities.

In lieu of a DMC, regular teleconferences with investigators will be held for reviewing reported safety data during the trial.

